9.4. Pattern Mixture Model

Patients are classified into four patterns for missing 6-MWT/KCCQ-OS data during the DB period:

1. Patients who died (including HT and LVAD placement) or unable to walk due to progression of ATTR amyloidosis (including hospitalization due to ATTR amyloidosis; applicable to 6-MWT only) before Month 30 visit: the missing change from baseline values at a postbaseline visit will be imputed as sampling with replacement from the worst 10% of observed change from baseline values from all patients at the same visit

and in same treatment group and same baseline tafamidis group, capped by the worst possible change for the patient (i.e. 0 – baseline value).

2. Patients in the vutrisiran arm who are not in Pattern 1 and have missing visits within 126 days of the last dose of vutrisiran: the missing change from baseline values are considered MAR and will be imputed using multiple imputation (MI) estimated from vutrisiran patients with non-missing data collected on treatment (i.e., data on visits within 126 days from last dose) in the same baseline tafamidis group. The window of 126 days is chosen as $1.5 \times$ the dosing interval of 84 days.
3. Patients in the vutrisiran arm who are not in Pattern 1 and have missing visits that are more than 126 days after the last dose of vutrisiran:
 - a. If there are sufficient (i.e., at least 10) retrieved dropouts at Month 30 in the same baseline tafamidis group, i.e., vutrisiran patients who discontinued treatment but still had assessment that are more than 126 days after the last dose, the missing data will be imputed using data from these retrieved dropouts.
 - b. If there are insufficient retrieved dropouts, missing change from baseline values will be assumed to be MNAR and imputed (using data from placebo patients in the same baseline tafamidis group) using the copy reference (CR) approach.
4. Patients in the placebo arm who are not in Pattern 1 and have missing data for other reasons:
 - a. If there are sufficient (i.e., at least 10) retrieved dropouts at Month 30 in the same baseline tafamidis group, i.e., placebo patients who discontinued study treatment but still had assessment that are more than 126 days from the last dose, the missing data will be imputed using data from these retrieved dropouts.
 - b. If there are insufficient retrieved dropouts, missing change from baseline values will be considered as MAR and imputed using MI estimated from all placebo patients in the same baseline tafamidis group.

Imputed change from baseline from any of the above methods will be capped by the worst possible change of the patient (0 – baseline value).

Details of MI:

For patients in Pattern 1, the imputation details are described above. For patients in Pattern 2 and Pattern 4b, all missing data for the placebo arm and missing data for the vutrisiran arm during the on-treatment period (ie, assessments within 126 days of the last dose of study drug) will be imputed using MI under the MAR assumption. Since the pattern of missing data within patients may be non-monotone, multiple imputation will be conducted separately by treatment arm and baseline tafamidis use group using the Markov Chain Monte Carlo (MCMC) method. For each treatment arm/baseline tafamidis use group, the imputation model will include type of amyloidosis (hATTR vs. wtATTR), NYHA class (I/II vs. III), age at randomization (<75 vs. ≥ 75), NT-proBNP (≤ 3000 ng/L vs > 3000 ng/L), baseline value, and all post baseline change from baseline values at protocol specified visits. The input dataset DATAIN will exclude data from vutrisiran patients that were collected after treatment discontinuation (ie, more than 126 days after the last dose of study drug). Below is a sample SAS code for the multiple imputation:

```
proc mi data=DATAIN out=DATA_STEP1 seed=xxx n impute=100;
  by treatment bltaf;
  em maxiter=300 converge=1e-4 itprint outem=outem;
  var baseline_variables base chg6m chg12m chg18m chg24m chg30m;
  mcmc chain=multiple initial=em;
run;
```

The MI procedure generates imputed values for all missing values. For patients in Pattern 1, the imputed data will be discarded and replaced by the imputed values using method described in Pattern 1 above. For vutrisiran patients, the imputed data from the on-treatment period will be kept while the imputed data after treatment discontinuation will be discarded and replaced by either the observed non-missing values (if available) or the imputed values using the CR approach described below (Pattern 3b). The imputation model is the same as that for Pattern 2 and 4.

```
proc mi data=DATA_STEP1_2 out=DATA_STEP2 n impute=1 seed=xxxx;
  by _imputation_ bltaf;
  class treatment;
  fcs nbiter=30 reg (chg30m = baseline_variables base chg6m chg12m chg18m
  chg24m);
  mnar model (chg30m / modelobs=(treatment='placebo'));
  var baseline_variables base chg6m chg12m chg18m chg24m;
run;
```

For imputation using the retrieved dropouts (Pattern 3a and 4a), the multiple imputation approach described in [Wang 2022] is adopted.

Combining Results

Missing values will be imputed 100 times to generate 100 complete datasets using the procedures described above (via MI, CR or other methods described above). An analysis of covariance (ANCOVA) model will be fit to each imputed dataset for the change from baseline in 6-MWT/KCCQ-OS at Month 30. The ANCOVA model will include baseline 6-MWT/KCCQ-OS as a covariate and treatment arm, baseline tafamidis use, treatment by baseline tafamidis use interaction, ATTR disease type, and age group as factors. For the vutrisiran monotherapy subgroup analysis, baseline tafamidis use, and treatment by baseline tafamidis use interaction will be removed from the model. The LS mean and SE estimated from the ANCOVA model fit to each imputed dataset will be combined by applying Rubin's rules,[Rubin 1996; Rubin 1987] using SAS PROC MIANALYZE to produce inferential results including the treatment difference in LS means, 95% CI for the treatment difference, and the p-value.

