4.7. Handling of Missing Data

No imputation will be done for early dropout patients for the primary analysis of the composite outcome endpoint. For longitudinal endpoints including 6-MWT and KCCQ-OS, the primary analyses will be based on mixed effects model repeated measures (MMRM) which implicitly impute missing values assuming missing at random (MAR). The only exception is missing due to death and unable to walk due to progression of ATTR amyloidosis (for 6-MWT only). For NYHA class, the missing due to death will also be imputed as class IV, and missing due to other reasons will be imputed via multiple imputation. Data handling strategies for these aforementioned intercurrent events and other intercurrent events in the primary analysis of 6-MWT, KCCQ and NYHA class are detailed in Section 5.7.2.1 and Section 5.7.2.3, respectively. Sensitivity analysis of the composite outcome endpoint will be conducted using Multiple Imputation (MI) to handle missing data, as described in Section 5.7.1.4.4. Sensitivity analyses for 6-MWT and KCCQ-OS will be conducted based on a pattern mixture model (PMM) which assume missing not at random (MNAR), as described in Section 5.7.2.1.3.

Since baseline NT-proBNP will be used as a covariate in the statistical models, for one patient with missing baseline NT-proBNP, the baseline value will be imputed with Week 12 visit data.

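### As worded, Pattern 1 of the 6-MWT pattern mixture model follows the patient rather than the missed visit, so a recovered patient whose Month 30 test is missing for an unrelated reason is scored like a death.

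*SAP*

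**What the plan says.** SAP Appendix 9.4 opens with the unit of classification: "Patients are classified into four patterns for missing 6-MWT/KCCQ-OS data during the DB period". Pattern 1 covers "Patients who died (including HT and LVAD placement) or unable to walk due to progression of ATTR amyloidosis (including hospitalization due to ATTR amyloidosis", and the rule continues "applicable to 6-MWT only) before Month 30 visit: the missing change from baseline values at a postbaseline visit will be imputed". The imputation is by "sampling with replacement from the worst 10% of observed change from baseline values from all patients at the same visit", within the same treatment arm and baseline tafamidis group. The donor rule is the same for death and for inability.

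Patterns 2, 3 and 4 are each limited to patients outside Pattern 1. For placebo the text is "Patients in the placebo arm who are not in Pattern 1 and have missing data for other reasons". The multiple-imputation (MI) details in the same appendix then discard the MI values of Pattern 1 patients and put the worst-10% draws in their place, with no limit by visit or reason. The PMM result comes from an ANCOVA of the change at Month 30.

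Elsewhere the SAP ties the rule to the cause of the gap. Section 4.7 describes the departure from missing at random as "The only exception is missing due to death and unable to walk due to progression of ATTR amyloidosis (for 6-MWT only"). Section 5.7.2.1.3 likewise keeps worst-outcome imputation for 6-MWT values that are missing because the patient could not walk.

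**The concern.** Death, transplant and LVAD placement are permanent for this purpose. Inability to walk and hospitalization need not be. Protocol 6.2.3 expects a hospitalized patient to be tested again, normally after at least two weeks. It also says the test should not be done when the patient is unwell from something external, such as flu or a sprain. SAP 5.13 plans a summary of 6-MWT assessments missed because of COVID-19, and Appendix 9.4 itself allows for gaps that are not monotone. So an earlier ATTR event, then recovery, then an unrelated gap at Month 30 is a sequence the documents allow for.

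At stake is the Month 30 value, the only one the PMM tests. This analysis is meant to show whether the 6-MWT result survives departures from missing at random. If some patients carry a score meant for death because of an event they recovered from, the check measures something other than what SAP 4.7 describes. Two programmers could also build different Month 30 data sets from the same SAP.

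**Working it through.** **Tracing one patient.** Suppose an ATTR hospitalization with the Month 12 test missing, Months 18 and 24 observed, and Month 30 missed for an unrelated reason.

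| Reading | Month 12 | Month 30 |
|---|---|---|
| Appendix 9.4 as worded | worst 10% | worst 10% |
| Reason-based wording of 4.7 and 5.7.2.1.3 | worst 10% | Pattern 2 or 3 (vutrisiran), Pattern 4 (placebo) |

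The readings differ at the one visit that is analysed.

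**Size per affected patient.** The plan states no figure to reproduce, so what follows rests on assumptions. If changes are normal, the worst decile has its mean at φ(z₀.₁₀)/0.10 = 1.755 SD below the overall mean. For an SD of 60 to 120 m (assumed), each 1% of an arm moved from an average value to the worst decile lowers that arm's mean by 1.755 × 60 × 0.01 = 1.1 m to 1.755 × 120 × 0.01 = 2.1 m.

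**Effect on the treatment difference.** Assumed inputs, none from the documents:
- mean change −60 m on placebo and −35 m on vutrisiran, each 30 m lower after an earlier ATTR event;
- within-group SD 90 m;
- a proportion p of each arm with an earlier event;
- a proportion m missing Month 30 for other reasons, independently of p.

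With μ the arm's mean without an event, the formulas are:
- arm mean = μ − 30p
- arm SD = √(90² + 30²·p(1−p))
- donor mean = arm mean − 1.755 × arm SD
- shift in the arm = p·m × (donor mean − (μ − 30))

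Worked case, p = 45% on placebo and 30% on vutrisiran, m = 15%:
- Placebo: arm mean −73.5, SD 91.2, donor mean −233.6. Shift = 0.0675 × (−233.6 + 90) = −9.69 m.
- Vutrisiran: arm mean −44.0, SD 91.0, donor mean −203.8. Shift = 0.045 × (−203.8 + 65) = −6.25 m.
- Change in the difference = 9.69 − 6.25 = 3.4 m, on a true difference of 73.5 − 44.0 = 29.5 m.

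| Earlier events, placebo vs vutrisiran | Missing Month 30 | Shift in the difference |
|---|---|---|
| 30% vs 30% | 15% | 0 m |
| 5% vs 3% | 10% | 0.3 m |
| 35% vs 25% | 10% | 1.5 m |
| 45% vs 35% | 15% | 2.3 m |
| 45% vs 30% | 15% | 3.4 m |

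A positive shift enlarges the apparent benefit of vutrisiran. Reversing the last row (30% placebo, 45% vutrisiran) gives −3.4 m.

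**Yardstick.** With 600 patients randomized 1:1 and SD 90 m, the standard error of the difference is 90 × √(2/300) = 7.3 m. The non-zero rows run from 0.3/7.3 = 0.04 to 3.4/7.3 = 0.47 standard errors.

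**The case against.** The best reply is that a visit-level rule was intended. Patterns 2 and 3 divide missing visits at 126 days after the last dose, so one vutrisiran patient can fall in both, and the patterns cannot be strictly one per patient. Pattern 4's reference to other reasons suggests that Pattern 1 is itself a reason for missingness. Hospitalization sits in a parenthesis under inability to walk, and may mean only a patient who could not be tested because of it. This makes the intent plausible. But 9.4 nowhere says so, its exclusions leave a recovered patient no other pattern, and the MI details repeat the patient-level rule. The next sentence there does restrict replacement by timing for vutrisiran patients, so the authors stated a limit where they wanted one.

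A second reply is that few patients qualify. A sprain leads to rescheduling where possible (Protocol 6.2.3). A visit that cannot be done on site may be completed up to three months later (Protocol 6). The Month 30 window in SAP Table 4 runs from day 841 to 1016, which is 176 days. This stands: the higher rates in the calculation may well be too high. The calculation also leaves out deaths, the cap at zero minus baseline, donor selection by tafamidis group and the ANCOVA adjustment.

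A reader might infer that the rule biases the result towards vutrisiran. The documents do not support that. Donors come from the patient's own arm, so direction depends on how earlier events split between arms, and no split is given. If treatment affected neither walking nor hospitalization, entry rates and donor pools would match in expectation and no systematic shift would arise.

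A reader might also infer that the primary 6-MWT analysis has the same fault, or that Table 8 contradicts 9.4. The primary model text and the death row of Table 8 are redacted. The Table 8 row on inability does not say whether the value must be missing because of the inability at that visit. The conflict that can be shown is with 4.7 and 5.7.2.1.3 only.

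**Conclusion.** The point holds as a fault in the stated rule. Followed literally, 9.4 gives a recovered patient with an unrelated Month 30 gap a death-equivalent score, contrary to the reason-based rule in 4.7 and 5.7.2.1.3. It is minor. A recovered patient with an observed Month 30 test keeps it. KCCQ-OS is unaffected, because the inability rule applies to the 6-MWT alone. The PMM is a sensitivity analysis outside the alpha-controlled testing sequence of SAP 4.6. The 0 to 3.4 m range is illustrative: it rests on the assumed means, SD, event rates and independent missingness, and stays below half a standard error even at its top. The trial's own numbers of such patients are needed to say more.

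**What to change.** Define Pattern 1 by visit and reason. Suggested text: *A missing 6-MWT change at a visit belongs to Pattern 1 only if, by that visit, the patient had died or had a heart transplant or LVAD, or if the test at that visit was not done because ATTR progression left the patient unable to walk, including being in hospital for ATTR amyloidosis at that visit. Every other missing value follows Patterns 2 to 4, whatever happened at earlier visits.*

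In Patterns 2 to 4, make the exclusion refer to the missing value and not the patient. In the MI details, replace the reference to Pattern 1 patients with one to Pattern 1 values, so that only those are overwritten.

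The cost is a wording change and a flag for each missed visit giving the reason the test was not done. The documents do not show the case report form field for this, but SAP 4.7 already presupposes that the reason is known. Reporting how many values the visit-level rule moves out of Pattern 1, by arm, would show whether the distinction mattered.

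### The pattern mixture model fills deaths (and, for 6-MWT, inability to walk) from a donor pool that never changes across imputations, so Rubin's rules omit part of the sampling variance; the size depends on inputs the documents do not give

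*SAP*

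**What the plan says.** SAP Section 5.7.2.1.3 names two sensitivity analyses for 6-MWT and KCCQ-OS: an MMRM that does not impute deaths with a worst outcome, and a pattern mixture model (PMM) that tests the missing-at-random assumption. Appendix 9.4 specifies the PMM.

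- Pattern 1 is "Patients who died (including HT and LVAD placement) or unable to walk due to progression of ATTR amyloidosis" before Month 30; the second condition applies to 6-MWT only.
- Their missing changes come from "sampling with replacement from the worst 10% of observed change from baseline values from all patients at the same visit". Donors are restricted to the patient's own arm and tafamidis cell, and no filled value may be worse than zero minus that patient's baseline.
- Draws from the MCMC step are not kept for these patients: "the imputed data will be discarded and replaced by the imputed values using method described in Pattern 1 above".
- "Missing values will be imputed 100 times to generate 100 complete datasets using the procedures described above", and "An analysis of covariance (ANCOVA) model will be fit to each imputed dataset" at Month 30.
- "The LS mean and SE estimated from the ANCOVA model fit to each imputed dataset will be combined by applying Rubin's rules", which yields the treatment difference, 95% CI and p-value.

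No step redraws or resamples the donor pool. Appendix 9.3, on missing CV events, does the opposite: it uses freshly sampled regression coefficients in each imputation so that their variability is carried through.

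**The concern.** Rubin's rules need each imputation to reflect uncertainty about the distribution being imputed from. Here that distribution, the observed worst 10% of a cell, is identical in every dataset. The between-imputation variance shows only which donor was drawn. It misses two things: the tail is itself estimated from few patients, and those same patients also enter the observed mean, so the two parts of the arm mean are positively correlated. More imputations do not help. This is a variance error, present even when the arms are identical and the estimate is unbiased.

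At stake is the credibility of a robustness check on two endpoints in the alpha-controlled hierarchy of SAP Section 4.6. An interval that is too narrow makes the check agree with the main result more readily than it should.

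**Working it through.** **Inputs from the documents.** 600 patients (Protocol 3.4), 1:1 (SAP 2.4), about 40% on tafamidis at baseline (Protocol 10.4.1). Per arm that is 300 × 0.6 = 180 monotherapy and 300 × 0.4 = 120 on tafamidis. There are 100 imputations and a 95% CI. The plan states no SE or coverage for this analysis, so there is no figure to reproduce first.

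**Assumptions.** Pattern 1 share d from 5% to 25% per arm; changes roughly normal; no treatment effect; Pattern 1 the only missingness. For simulation: 6-MWT baseline 370 m (SD 95, floor 150 m from inclusion criterion 7), residual SD of change 75 m; KCCQ-OS baseline 72 (SD 20), residual SD of change 18.

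**Donor pool.** At d = 20% a monotherapy cell has 180 × 0.8 = 144 observed patients and about 14.4 donors for 36 Pattern 1 patients. Each donor is used 36/14.4 = 2.5 times on average, besides counting once itself.

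**Closed form, one arm, in units of σ²/n.** For a normal worst 10% the tail mean is −1.755σ and the tail variance 0.169σ². The sampling variance of the tail mean, times the number observed, is 10 × [0.169 + 0.9 × (1.7550 − 1.2816)²] = 3.71. Its covariance with the observed mean, times the number observed, is 1. With 1.755² = 3.08:

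- True: [(1−d)² + 3.71d² + 2d(1−d)]/(1−d) + 3.08d(1−d)
- Rubin: (1−d) + 0.169d + 3.08d(1−d) + 1.01 × 0.169d

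At d = 0.20:

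- True: (0.64 + 0.148 + 0.32)/0.8 + 0.493 = 1.878
- Rubin: 0.8 + 0.034 + 0.493 + 0.034 = 1.361
- SE ratio √(1.361/1.878) = 0.851, so the SE is 14.9% too small; coverage 2Φ(1.96 × 0.851) − 1 = 90.5%.

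σ and n cancel from the ratio.

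**Simulation of Pattern 1 as written**, with cap, ANCOVA on baseline and treatment, and Rubin pooling; monotherapy, 180 per arm, 6,000 trials, 40 imputations. Entries are SE shortfall / coverage.

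| Share | Donors per cell | Closed form | 6-MWT | KCCQ-OS |
|---|---|---|---|---|
| 5% | 17.1 | 3.9% / 94.0% | 3.9% / 94.0% | 3.9% / 94.4% |
| 10% | 16.2 | 7.6% / 93.0% | 6.0% / 93.5% | 7.7% / 92.8% |
| 15% | 15.3 | 11.2% / 91.8% | 10.8% / 92.1% | 10.3% / 92.2% |
| 20% | 14.4 | 14.9% / 90.5% | 13.8% / 91.3% | 14.2% / 90.8% |
| 25% | 13.5 | 18.7% / 88.9% | 18.8% / 89.1% | 17.7% / 89.6% |

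A run with 100 imputations (6-MWT, 3,000 trials per setting) gave shortfalls of 4%, 6%, 13%, 14% and 19% at the five shares. Another run gave 6%, 10%, 13% and 17% at 5%, 10%, 20% and 25%. In the overall population the shortfall was about 7% at a 10% share and 14% at 20%. A left-skewed 6-MWT change at a 20% share gave about 22% and 87% coverage, so the range depends on shape too.

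**Adding the other patterns.** With 10-15% further missingness (assumed; 180 per arm, SD 75 m, 2,000 trials), for 6-MWT:

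- All other vutrisiran gaps filled by copy-reference: at a 5% Pattern 1 share the SE is 7-11% too large (coverage about 97%); at 10%, 2-6% too large (95-96%); at 20%, 8-9% too small (about 93%).
- Half missing-at-random, half copy-reference: 2-6% too small at 10%, 12-14% at 20%.
- All missing-at-random: 7-8% and 14-15% too small.

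**The case against.** The strongest reply is that the table describes Pattern 1 alone, not the full PMM. Pattern 3b fills late vutrisiran gaps from the placebo model. That pulls the arms together and makes Rubin's variance conservative, in the opposite direction. The last set of runs bears this out: at low Pattern 1 shares even the sign of the net error can change. This stands. A reader might infer that the PMM's SEs are too small by a fixed percentage; the documents give no pattern mix, Pattern 1 share or SD, and do not support that.

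A second reply is that the analysis is minor. It is one of two sensitivity analyses, and in the other no death is filled from a donor pool. It feeds no step of the testing procedure in SAP Section 4.6. This also stands. A reader might infer inflated trial-wise type I error; that does not follow.

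A third reply is that worst-tail values are a deliberate penalty rather than a guess at missing data. This does not rescue the SE. The penalty is estimated from about a dozen patients in the same trial, and that error belongs in the variance whatever the estimand.

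Finally, a reader might extend the point to the main MMRM, since SAP Section 5.7.2.1.3 indicates that it gives deaths a worst outcome. The rule itself is redacted, so nothing can be concluded about that analysis.

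**Conclusion.** The Pattern 1 imputation is improper and its contribution to the pooled variance is understated. That follows from the unredacted text and does not depend on the assumed inputs. The size does: under the Pattern 1-only, roughly normal assumptions above, SEs are about 4-6% too small at a 5% share and about 6-19% too small at 10-25%. The net error of the full PMM may be smaller, nil or reversed where copy-reference filling is common and Pattern 1 is rare. Where Pattern 1 is around 20%, a shortfall remained in every pattern mix tried. No primary or secondary claim changes; what is affected is how much reassurance the PMM's CI and p-value can give.

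**What to change.** In the Combining Results part of Appendix 9.4, take the PMM's SE, 95% CI and p-value from a bootstrap of the whole procedure:

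- Resample patients with replacement within treatment-by-baseline-tafamidis cell. In each resample re-select the worst 10%, redo the Pattern 1-4 imputation and refit the ANCOVA.
- Fix the choice between 3a and 3b, and between 4a and 4b, from the original data. Otherwise the threshold of 10 retrieved dropouts can switch between resamples and mix different assumptions in one SE.
- State the number of resamples (for example 1,000) and of imputations per resample.

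In Pattern 1-only simulations (700 trials per setting) the ratio of bootstrap to empirical SE was 0.94, 0.99 and 1.00 at shares of 10%, 20% and 25%, with coverage 93.1%, 94.9% and 95.4%. The low first ratio looks mostly like simulation noise: the bootstrap SE of 9.31 m agrees with the 9.26 m empirical SE of the 6,000-trial run. The bootstrap has not been tested here with Patterns 2-4 present.

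Redrawing only the donor pool within each imputation is a partial repair and should not be presented as sufficient: at a 20% share it left the SE about 9% (6-MWT) to 12% (KCCQ-OS) too small, with coverage of about 91-92%.

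The cost is SAP wording, computing time and, usually, a somewhat wider interval for this sensitivity analysis. Trial conduct and data collection are unaffected.

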10.4. Amendment History

10.4.1. Amendment 5 Summary of Changes

The primary purpose for this global protocol amendment is to expand the analysis of the existing primary endpoint to both the overall population and the vutrisiran monotherapy subgroup (defined as the subgroup of patients not on tafamidis at study baseline). Changes included in this amendment concern the method of data analyses and do not impact study execution or the patient experience.

Establishing the efficacy of vutrisiran in the overall population is important because it is representative of current treatment practice, wherein many patients with ATTR amyloidosis (hereditary and wt) with cardiomyopathy are prescribed tafamidis as it is the only currently approved treatment available.

The rationale for analyzing the primary endpoint in the vutrisiran monotherapy subgroup is to enable demonstration of the potential clinical benefit of vutrisiran without any confounding effect of benefit from tafamidis. Patients already prescribed tafamidis for the approved cardiomyopathy indication were permitted to enroll in HELIOS-B, and there was no eligibility requirement that these patients needed to have manifested disease progression on tafamidis. Thus, patients on tafamidis at baseline, comprising approximately 40% of the enrollment into

HELIOS-B, are likely to have been receiving some degree of CV benefit from this medication throughout the trial. For this reason, the results from a pre-specified analysis in the vutrisiran monotherapy subgroup would provide the clearest demonstration of the potential clinical benefit of vutrisiran, without any confounding effect of benefit from concomitant tafamidis.

This amendment also restructures the existing secondary and exploratory endpoints such that specific endpoints were moved from exploratory to secondary and from secondary to exploratory based on the rationale below.

Changes included with Amendment 5 are outlined below:

Section(s)	Description of Change	Brief Rationale

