5.7.2.1.3. Sensitivity Analysis

An alternative estimand is to estimate the changes from baseline and treatment effects at scheduled visits for patients who were alive at the visits. The analysis will be based on the same MMRM model as the primary analysis with different ICE handling strategy for death. Missing data due to death will not be imputed with worst outcome and will be assumed as MAR. For 6-MWT, missing due to unable to walk due to progression of ATTR amyloidosis will still be imputed with worst outcome, the same as in the primary analysis.

A sensitivity analysis using PMM will also be performed to assess the robustness of the primary MMRM results to the possible violation of the MAR missingness assumption. The PMM accommodates situations where the missingness mechanism may be MNAR. Unlike the primary analysis, this sensitivity analysis imputes the missing data based on different missing patterns. More details on the PMM are provided in Appendix 9.4.

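### The 6-MWT/KCCQ-OS pattern mixture model separates on-drug from off-drug gaps for vutrisiran but not for placebo, so placebo patients still being dosed can be imputed from dropouts alone

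*SAP*

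**What the plan says.** SAP 9.4 sets aside deaths and, for 6-MWT, inability to walk from disease progression (Pattern 1). It then sorts the remaining missing values by arm.

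- **Vutrisiran, on treatment (Pattern 2):** "Patients in the vutrisiran arm who are not in Pattern 1 and have missing visits within 126 days of the last dose of vutrisiran". These are treated as missing at random, with on-treatment vutrisiran patients in the same tafamidis group as donors.
- **Vutrisiran, off treatment (Pattern 3):** visits beyond 126 days. Retrieved dropouts are the donors if there are at least 10; otherwise copy reference is used.
- **Placebo (Pattern 4):** "Patients in the placebo arm who are not in Pattern 1 and have missing data for other reasons". Time since last dose is not a condition. With at least 10 retrieved dropouts (4a), the donors are "placebo patients who discontinued study treatment but still had assessment that are more than 126 days from the last dose". With fewer (4b), values are "imputed using MI estimated from all placebo patients in the same baseline tafamidis group".

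The Details of MI keep the asymmetry: "The input dataset DATAIN will exclude data from vutrisiran patients that were collected after treatment discontinuation". No matching exclusion is written for placebo. SAP 5.7.2.1.3 gives the purpose of the analysis: "to assess the robustness of the primary MMRM results to the possible violation of the MAR missingness assumption".

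**The concern.** Take two patients still receiving study drug who each miss the Month 30 walk test. The vutrisiran patient's value is drawn from on-treatment vutrisiran patients. If 4a applies, the placebo patient's value is drawn only from placebo patients who stopped treatment more than 126 days earlier. The reason for the gap is the same, but the donors differ by arm.

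People who stop treatment may well differ in outcome from those who continue. If they do worse, the rule lowers the placebo mean and moves the estimate toward vutrisiran without any drug effect. If they do better, for example after starting another therapy, it moves the other way. A check on whether the MMRM result survives departures from missing at random should not contain a shift that comes from the donor rule. Pattern 3b can push in the opposite direction for an effective drug, but it concerns different patients and does not correct this.

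**Working it through.** **1. The plan's own figure.** 1.5 × 84 days = 126 days. The window reproduces exactly.

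**2. Donors as written.**

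| Gap outside Pattern 1 | Vutrisiran donors | Placebo donors |
|---|---|---|
| Within 126 days of last dose | On-treatment vutrisiran | Placebo dropouts only (4a) or all placebo (4b) |
| Beyond 126 days | Vutrisiran dropouts (3a) or copy reference (3b) | Same as the row above |

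The Details of MI refer to all missing placebo data, but that sentence is confined to Patterns 2 and 4b. The appendix then sends 4a to a separate retrieved-dropout method. Nothing directs on-treatment placebo gaps to on-treatment placebo donors.

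**3. How often 4a applies.** About 600 patients are planned, randomized 1:1, with "patients on tafamidis at baseline, comprising approximately 40% of the enrollment into" the study (Protocol 10.4.1). That gives 600 × 0.6 / 2 = 180 placebo patients without baseline tafamidis and 600 × 0.4 / 2 = 120 with it. Ten dropouts are 5.6% and 8.3% of these. The documents give no discontinuation or retrieval rates, so these are assumed: 12% off drug and two-thirds retrieved, or 8%.

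- Binomial P(X ≥ 10), n = 180, p = 0.08: 0.92
- Binomial P(X ≥ 10), n = 120, p = 0.08: 0.49
- With 10 to 20% off drug and half to two-thirds retrieved: 0.41 to above 0.99 (n = 180) and 0.08 to 0.97 (n = 120)

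**4. Size of the shift, 6-MWT, no treatment effect.** All inputs are assumptions: SD 80 m, correlation between visits 0.75, 12% off drug, a proportion *m* = 5 to 15% of on-treatment patients missing Month 30, and dropouts *d* = 20 to 40 m worse at Month 30 and half as far behind at the prior visit. The missing value is imputed by regression on the prior visit within the donor set. A hand approximation when 4a applies is:

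shift ≈ 0.88 × *m* × *d* × (1 − 0.75 × 0.5)

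- *m* = 0.05, *d* = 20: 0.88 × 0.05 × 20 × 0.625 = 0.55 m
- *m* = 0.10, *d* = 40: 0.88 × 0.10 × 40 × 0.625 = 2.2 m
- *m* = 0.15, *d* = 40: 0.88 × 0.15 × 40 × 0.625 = 3.3 m

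Simulation (3000 trials per setting, 20 imputations, written rule and split rule applied to the same data) agrees:

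| Setting | Shift toward vutrisiran |
|---|---|
| 4a applies | +0.5 to +3.3 m |
| 4a applies, dropouts fully behind, or not behind at all, at the prior visit | +0.1 to +5.4 m |
| 4b applies | 0 to +0.4 m |
| Averaged over the trigger, no baseline tafamidis | +0.5 to +3.0 m |
| Averaged over the trigger, baseline tafamidis | +0.3 to +1.7 m |
| 4a applies, dropouts 20 m better | −0.5 to −1.7 m |
| Pattern 4 split at 126 days | 0 within simulation error |

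At *m* = 2%, the formula gives 0.2 m (*d* = 20) to 0.4 m (*d* = 40).

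**The case against.** **Stopping saline removes no drug effect, so placebo needs no split.** This is true of the drug effect, but it argues for pooling all placebo patients, as 4b does. It does not support using dropouts alone.

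**The 4a model is in a cited paper that was not available.** It may condition on treatment status. This stands as a limit on the figures, since regression on the prior visit is a substitute. The donor set, however, is stated in the SAP itself. The code description also gives no step that replaces placebo values under 4a, so clarification is needed in any case.

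**Few patients are affected.** The final ANCOVA uses Month 30 only, the Month 30 window runs from day 841 to day 1016 (SAP Table 4), and patients unable to walk because of progression go to Pattern 1. On-treatment gaps may therefore be nearer 2% than 5 to 15%. This stands, and the shift would then be under half a metre.

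**The trigger is overstated.** Dead patients cannot be retrieved. If 20% are removed (an assumption) and 8% is kept among the rest, the probabilities fall to 0.72 (n = 144) and 0.24 (n = 96). This is fair, and both lie inside the ranges in step 3.

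**The shift is small against noise.** At SD 80 m, the unadjusted standard error is 80 × √(2/180) = 8.4 m or 80 × √(2/120) = 10.3 m. The trigger-averaged shifts are about 0.03 to 0.36 of that. This also stands, but the shift is systematic and costs little to avoid.

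**Conclusion.** The concern holds. As written, placebo patients still on study drug are imputed from dropouts only once their tafamidis group has 10 retrieved dropouts, while on-drug vutrisiran patients never are. For 6-MWT the effect is probably at most a few metres when 4a applies, and close to zero if on-treatment gaps are rare or 4b applies. Size and sign rest on assumed missing-data rates, dropout outcomes and imputation model, because the documents give none of these. No size was worked out for KCCQ-OS. The analysis is a sensitivity analysis of two secondary endpoints and carries no alpha, so the MMRM, the primary endpoints and the testing procedure are untouched. The change is recommended rather than essential, with medium confidence.

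**What to change.** Split Pattern 4 at 126 days, mirroring Patterns 2 and 3:

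- **Placebo gaps within 126 days of the last dose:** multiple imputation under missing at random from on-treatment placebo patients in the same tafamidis group.
- **Placebo gaps beyond 126 days:** 4a if there are at least 10 retrieved dropouts, otherwise 4b.
- **Details of MI:** for the on-treatment step, exclude data more than 126 days after the last dose in both arms. Keep the full placebo data for 4b and for copy reference in 3b.
- **Reporting:** give the number of patients imputed under each pattern, by arm and tafamidis group.

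A simpler alternative is to send on-treatment placebo gaps to 4b. That would remove nearly all of the shift but leave a small mismatch in donors.

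The cost is a few SAP lines and one further imputation step, with no new data. The downside is that fewer placebo values are imputed away from missing at random, and the sensitivity estimate may be slightly less favourable to vutrisiran.
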